6.2.1 Efficacy

The analysis visit windows for efficacy endpoints are defined as follows:

Table 6-2 Efficacy Analysis Visit Definitions

Analysis Phase	Analysis Visit (Derived)	Target/Study Visit (eCRF)	Window
Pretreatment	Baseline	Day 1/Visit 2	Treatment Day ≤ 1 , pre-dose
Treatment	Week 1	Day 8/Visit 3	Treatment Day [6, 11]
	Week 2	Day 15/Visit 4	Treatment Day [12, 21]
	Week 4	Day 29/Visit 5	Treatment Day [22, 42]
	Week 8	Day 57/Visit 6	Treatment Day [43, 70]
	Week 12	Day 85/Visit 7	Treatment Day [71, last dose + 14
		•	days]

6.2.2 Safety

The analysis visit windows for safety endpoints are defined as follows (note that not all safety endpoints are collected at each visit):

Table 6-3 Safety Analysis Visit Definitions

Analysis Phase	Analysis Visit (Derived)	Study Visit (eCRF)	Window
Pretreatment	Baseline	Day 1/Visit 2	Treatment Day ≤ 1

Analysis Phase	Analysis Visit (Derived)	Study Visit (eCRF)	Window
Treatment	Week 1	Day 8/Visit 3	Treatment Day [6, 11]
	Week 2	Day 15/Visit 4	Treatment Day [12, 21]
	Week 4	Day 29/Visit 5	Treatment Day [22, 42]
	Week 8	Day 57/Visit 6	Treatment Day [43, 70]
	Week 12	Day 85/Visit 7	Treatment Day [71, last dose + 14
			days]

Local dermal tolerability data will be collected both pre-dose and post-dose at day 1 (visit 2)

6.3 Missing/Incomplete Date Conventions

Dates may be imputed with year, month, and day values under certain scenarios:

Table 6-4 Imputation Scenarios

		Complete		
Scenario	Year	Month	Day	Imputable
1	Yes	Yes	Yes	Complete
2	Yes	Yes	_	Yes
3	Yes	_	Yes	No ¹
4	Yes	_	_	Yes
5	_	Yes	Yes	No ¹
6	_	Yes	_	No ¹
7	_	_	Yes	No ¹
8	_	_	_	Yes

¹ Not allowed per database design.

Dates will be imputed initially toward a specified target date for imputable scenarios 2, 4, and 8, and adjusted against the latest reasonable dates. The initial imputed date is determined by the following algorithm:

Table 6-5 Initial Imputed Date Algorithm

Available Year		Available Month (MM)		
(YYYY)	Missing	< Target Month	= Target Month	> Target Month
Missing	Target Date		_	
< Target Year	YYYY-12-31	YYYY-MM-LD		
= Target Year	Target Date	YYYY-MM-LD	Target Date	YYYY-MM-01
> Target Year	YYYY-01-01	YYYY-MM-01		

YYYY = available start date year; MM = available start date month; LD = last day of the month.

6.3.1 Missing/Incomplete AE Start Date

AE start dates will be imputed as the minimum of the following:

- Initial imputed date, where target date = Treatment start date
- Complete end date

6.3.2 Missing/Incomplete Medication Start Date

Medication start dates will be imputed as the minimum of the following:

- Initial imputed date, where target date = Treatment start date -1
- Complete end date

6.3.3 Missing/Incomplete AE/Medication End Date

AE and medication end dates will be imputed as the minimum of the following:

- Initial imputed date, where target date = Treatment end date + 28
- Death date

6.4 Safety Endpoint Conventions

6.4.1 Adverse Events

6.4.1.1 Missing Intensity or Relationship

If the investigator is unable to provide the actual values, the following imputations will be applied:

Table 6-6 Missing AE Intensity and Relationship Imputation Algorithms

Missing Value	Imputation	Timing
Intensity	Mild Screening Period, Pretreat	
	Severe	Treatment Period
Relationship		Screening Period, Pretreatment Period
	Related	Treatment Period

6.4.2 Vital Signs

6.4.2.1 Continuous Descriptives Parameters

The following vital sign parameters will be summarized:

Table 6-7 Vital Sign Descriptive Parameters

Parameters			
Systolic blood pressure (mmHg)	Diastolic blood pressure (mmHg)	Heart rate (bpm)	
Respiratory Rate (bpm)	Body temperature (°C)	Weight (kg)	
Height (cm)			

6.4.3 Local Dermal Tolerability

The following local dermal tolerability parameters will be summarized:

Table 6-8 Local Dermal Tolerability Parameters

Parameter	Grade			
Stinging/burning	Prickling pain sensation immediately after (within 5 minutes of dosing, except baseline;			
	patient-rated):			
	• None (0) = No stinging/burning			
	• Mild (1) = Slight warm, tingling/stinging sensation; not really bothersome			
	• Moderate (2) = Definite warm, tingling/stinging sensation that is somewhat			
	bothersome			
	• Severe (3) = Hot, tingling/stinging sensation that has caused definite discomfort			
Dryness	Brittle and/or tight sensation (investigator- or designee rated):			
	• None (0) = No dryness			
	• Mild (1) = Slight but definite roughness			
	• Moderate (2) = Moderate roughness			
	• Severe (3) = Marked roughness			
Scaling	Abnormal shedding of the stratum corneum (investigator- or designee rated):			
	• None (0) = No scaling			
	 Mild (1) = Barely perceptible shedding, noticeable only on light scratching or rubbin 			
	Moderate (2) = Obvious but not profuse shedding			
	• Severe (3) = Heavy scale production			
Erythema	Abnormal redness of the skin (investigator- or designee rated):			
	• None (0) = No erythema			
	• Mild (1) = Slight pinkness present			
	 Moderate (2) = Definite redness, easily recognized 			
	• Severe (3) = Intense redness			

6.5 Imputed Value Listing Conventions

Missing data will not be imputed and listings will present the actual partial or missing values as they appear on the eCRFs.

7. References

No references are cited in this document.

8. Amendment(s)

The following changes have been made and comprise Amendment 1 of this document:

Changes:

- Section 5.1.1.1.1: The PK analysis population has been removed as this will be defined and discussed in a separate PK analysis plan.
- Section 6.4.2.1: Weight (kg) and height (cm) have been added as vital signs parameters to be analyzed. As this is a pediatric study, it is important to review these parameters and any changes from baseline to Week 12.
- Throughout the document, undefined link errors have been corrected.

ALLERGAN

16.1.9 Analysis Plan Prior to Database Lock 1679-401-006

Date (DD/MMM/YYYY)/Time (PT)	Signed by: Justification	
10-May-2018 12:56 GMT-07	PPD	PPD Approval
10-May-2018 14:54 GMT-07	PPD	PPD Approval
10-May-2018 15:47 GMT-07	PPD	PPD Approval
10-May-2018 16:00 GMT-07	PPD	PPD Approval

NON-CLINICAL AND TRANSLATIONAL SCIENCES

CLINICAL PHARMACOLOGY

A Pharmacokinetic Data Analysis Plan (DAP) for Study 1679-401-006 Entitled "An Open-Label Phase 4 Safety and Efficacy Trial of ACZONE (Dapsone) Gel, 7.5% in 9 to 11 Year-Old Patients With Acne Vulgaris"

Document Number	1679-401-006 -DAP		
Project Name and Number:	ACZONE (Dapsone, AGN-225678) Gel, 7.5% / 1679		
Protocol Number:	1679-401-006		
Phase:	4		
Clinic Start Date:	October 27, 2016		
Study Clinical Pharmacologist:	PPD		
Sponsor:	Allergan plc		

1 Table of Contents

1	Table of Contents	2
2	List of Abbreviations.	3
3	Introduction	4
4	Objectives	4
5	Methods	4
5.1	Study Design	4
5.2	Analysis Populations	7
5.3	Sample Size Considerations.	7
5.4	Software	7
5.5	Methodology of Measurements	7
5.5.1	Pharmacokinetic Methodology	7
5.6	Data Handling and Storage	8
6	Data Analysis	9
6.1	Pharmacokinetics	9
7	Statistical Analysis	9
7.1	Statistical Summarization	9
8	Presentation of Final Results	9
9	References	9

2 List of Abbreviations

ADaM Analysis Data Model

BLQ Below Limit of Quantitation

CRF Case Report Form

CSR Clinical Study Report

DAP Data Analysis Plan

DHA Dapsone Hydroxylamine

NAD N-acetyl Dapsone

PD Pharmacodynamic

PK Pharmacokinetic

SDTM Study Data Tabulation Model

sFTP secure File Transfer Protocol

3 Introduction

The data analyses outlined in this document are to support clinical study 1679-401-006.

In this study, measurements will be made for plasma concentrations of dapsone, N-acetyl dapsone (NAD), and dapsone hydroxylamine (DHA). This data analysis plan (DAP) outlines how data analysis of these measurements will be conducted. Additional analyses may be conducted if necessary.

4 Objectives

The objectives of this study are:

- To evaluate the safety and tolerability of ACZONE 7.5% administered topically oncedaily for 12 weeks in 9 to 11 year-olds with acne vulgaris.
- To evaluate the peak and trough plasma drug concentrations in 9 to 11 year-olds with acne vulgaris following once-daily dosing of ACZONE 7.5% under maximal use conditions for the first 8 days (+ 2 days).
- To explore the efficacy of ACZONE 7.5% administered topically once-daily in 9 to 11 year-olds with acne vulgaris.

5 Methods

5.1 Study Design

This study is a multicenter, open label, non-comparative, 12-week trial to evaluate the safety, tolerability, pharmacokinetics, and efficacy of ACZONE 7.5% in 9 to 11 year-old patients with mild, moderate, or severe acne vulgaris.

Patient participation is up to approximately 16 weeks. Patients will attend up to the following 7 visits: Screening, Baseline/Day 1 (Screening and Baseline/Day 1 may be combined if no washout is needed), and Weeks 1, 2, 4, 8, and 12/early exit. The total treatment duration of trial participation for each patient is up to 12 weeks. Safety measures include adverse events, physical examination, and vital signs. Efficacy measures include the Investigator's Global Assessment (IGA) and lesion counts in the face.

The 2 cohorts will enroll concurrently; the PK cohort and the non-PK Cohort.

The PK Cohort will include at least 16 evaluable PK patients. Evaluable PK patients are defined as those that are administered at least 8 applications of study drug under maximal use conditions, and have provided evaluable PK samples for analysis without any major protocol deviations. For the first 8 days, study drug will be administered once-daily under maximal use condition (~2 grams/day) to the entire face, neck, upper chest, upper back and shoulders as instructed by the study site. The study drug should be rubbed in gently and completely. On Day 1, the study drug will be administered on-site. From Day 2 through Day 7, the study drug will be administered in the morning at home by the patient's legally authorized representative. At the Week 1/Visit 3 [Day 8 (+2 days)], the study drug will be administered on-site in the morning. Also at the Week 1/Visit 3 visit, blood samples will be collected at 2 timepoints 1) prior to dosing, and 2) approximately 10 hours post dose (\pm 3 hours). This collection scheme is designed to minimize the number of blood draws in this challenging patient population while still being able to determine the peak and trough plasma concentrations of dapsone, NAD, DHA, and other metabolites or analytes (if warranted) for steady-state pharmacokinetic assessment. This limited blood collection scheme is appropriate as the systemic drug concentrations of dapsone at steady state were reached after 7 days and appeared to be relatively constant in male and female acne patients 11 years of age or older following once daily topical administration of Dapsone 7.5% Gel under maximal use conditions for 28 days (Study 225678-004). Similarly, steady-state systemic concentrations of dapsone metabolites were also relatively constant.

After the Week 1/Visit 3, patients or the patient's legally authorized representative will apply a pea-sized amount of study drug in a thin layer to the patient's face, once-daily, at home for the remaining 11 weeks, the same as the dose regimen for the Non-PK Cohort. Acne-affected areas on the upper chest, upper back, and shoulders should also be treated with a thin layer during the final 11 weeks.

For the Non-PK Cohort (approximately 84 patients), patients or the patient's legally authorized representative will apply a pea-sized amount of study drug in a thin layer to the patient's face once-daily at home for 12 weeks as instructed by the study site. Acne-affected areas on the upper chest, upper back, and shoulders should also be treated with a thin layer.

Study Period	Screening	Baseline/Day 1ª	Week 1	Week 2	Weeks 4 and 8	Week 12/ Early Exit
Visit Number	Visit 1	Visit 2	Visit 3	Visit 4	Visit 5 and Visit 6	Visit 7
Visit Windows	Day -30 to Day -1	N/A	Day 8 (+ 2 days)	Day 15 (± 3 days)	Day 29 (± 7 days) and Day 57 (± 7 days)	Day 85 (± 7 days)
Informed consent/authorization and minor assent ^b	X					
Inclusion/exclusion criteria	X	X				
Medical/surgical history	X					
Demographics	X					
Skin phototype assessment	X					
Physical examination includes vital signs, height and weight ^c	X					X
Pregnancy test (urine) ^d	X	X			X	X
IGA	X	X	X	X	X	X
Lesion count	X	X	X	X	X	X
Enrollment		X				
PK Cohort: Dispense study drug, training on application/return ^e		D	R/D		R/D	R
Non-PK Cohort: Dispense study drug, training on application/return ^f		D			R/D	R
Standardized photographs ^g		X				X
Local tolerability ^h		X	X	X	X	X
Concomitant medications	X	X	X	X	X	X
Concomitant procedures	X	X	X	X	X	X
Adverse events	X	X	X	X	X	X
PK sampling ⁱ			X			

D = dispense; IGA = Investigator's Global Assessment; N/A = not applicable; R = return; PK= pharmacokinetic

^a If a washout period is not required, then screening and baseline visits can occur on the same day, and the procedures required to be repeated at both visits should be performed once.

b Consent for photography is included in the informed consent process at select centers.

Physical examination and vital signs are to be performed if inclusion/exclusion criteria are met at screening; not required for screen failures. Vital signs include heart rate, blood pressure, respiratory rate, and body temperature.

^d Female patients only. The urine pregnancy test can also be performed at any timepoint during the course of the trial at the investigator's discretion. If a patient misses a menstrual cycle, a urine pregnancy test must be performed.

Patients in the PK cohort will be dispensed 1 kit with 14 tubes on Baseline/Day 1 (Visit 2). All patients in the PK cohort will start dosing on Day 1 using the 2.0 gram tubes dispensed for individual application.PK Cohort patients will return used study drug at Week 1/Visit 3. At Week 1/Visit 3, Week 4 (Visit 5) and Week 8 (Visit 6) the patients in the PK Cohort are dispensed 60-gram pumps. Dispensed and returned study drug will be weighed at the study center.

f All patients will start dosing on day 1. The patients in the Non-PK Cohort are dispensed 60-gram pumps on Baseline/Day 1 (Visit 2), Week 4 (Visit 5) and Week 8 (Visit 6). Dispensed and returned study drug will be weighed at the study center.

At select centers, patients may have photographs taken of their face for illustration or presentation purposes. Patients who consent to being photographed will be required to remove any make-up at least 20 minutes prior to having photographs taken.

Local tolerability will be assessed prior to drug administration on day 1, as well as postdose on the face only.

Only applies to patients in the PK Cohort at the Week 1/Visit 3. Blood samples will be collected within 30 minutes prior to dosing in clinic in the morning and at approximately 10 hours post dose (± 3 hour) (patients are allowed to leave and come back if needed) under maximal use conditions to determine the peak and trough plasma drug concentrations.

5.2 Analysis Populations

The following 3 analysis populations will be utilized:

- 1. The safety population includes all patients who are treated with at least one application of study drug.
- 2. The modified intent-to-treat (mITT) population includes all enrolled patients who have a baseline assessment and at least one post-baseline assessment.
- 3. The PK population will be defined as all patients who received applications of study drug for at least 8 days under maximal use conditions and have evaluable blood samples for PK analysis.

Safety analyses will be based on the safety population. Efficacy analyses will be based on the mITT population. PK analyses will be based on the PK population.

5.3 Sample Size Considerations

The FDA approval of ACZONE 7.5% included a post-marketing requirement (PMR 3017-1) to assess the product in patients 9 to 11 years of age, including pharmacokinetic (PK) evaluation in a subset of patients. The sample size for the trial was determined empirically, and is consistent with that requested by the FDA in the postmarketing requirement for ACZONE 7.5% (FDA Letter, 2016).

5.4 Software

Descriptive statistics of plasma concentrations will be calculated with the software program Phoenix® WinNonlin® (version 6.3 or newer)

5.5 Methodology of Measurements

5.5.1 Pharmacokinetic Methodology

For patients in the PK Cohort who will be dosed under maximal use conditions for the first 8 days, blood samples will be collected within 30 minutes prior to dosing (in the clinic in the morning) and at approximately 10 hours post dose (± 3 hours) at the Week 1/Visit 3 [Day 8 (+ 2 days)] to determine the peak and trough plasma concentrations of dapsone, NAD, DHA, and other metabolites or analytes (if warranted). Blood will be collected in 2 mL prechilled K3EDTA tubes, chilled for 20-30 minutes in an ice water bath and centrifuged within 30

minutes of blood draw at no less than 2000g for 10 minutes. For sites with a refrigerated centrifuge, centrifugation will occur at approximately 4°C; for sites without a refrigerated centrifuge, rotors or buckets will be chilled in a refrigerator overnight. After centrifugation, the plasma samples will be harvested and transferred into 2 prechilled, coded polypropylene tubes. The samples will then be flash-frozen in a dry ice and alcohol bath and stored at approximately –20°C until shipment to PPD . Details on PK collection, processing and storage can be found in the laboratory manual.

Plasma concentrations of dapsone, NAD, DHA, and other metabolites or analytes (if warranted) will be determined using a validated liquid chromatography-tandem mass spectrometry method.

5.6 Data Handling and Storage

will transfer the samples to PPD , which will determine plasma concentrations of dapsone, DHA, and NAD. A source data file from PPD will be transferred to Allergan Clinical Data Management group's server via secure File Transfer Protocol (sFTP). Allergan Data Management will use the data for reconciliation against case report form (CRF) data and general cleaning. Allergan Statistical Science and Programming and PPD will generate SDTM and ADaM PK datasets per SDTM and ADaM specifications. Allergan Statistical Science and Programming group will provide the ADaM PK dataset to Allergan Global Clinical Pharmacology group via a shared folder such as BOX.

Pharmacokinetic analysis and statistical analysis of pharmacokinetic data will be performed using Pharsight Phoenix WinNonlin (version 6.3 or newer), SAS[®] (version 9.3 or newer), or other appropriate software. Electronic data will be archived on a secure computer server.

Unless otherwise specified in subsequent sections, the general data handling include the following:

- All measured data will be used in analysis initially unless it may be excluded in accordance to regulatory guidances. Measured data not used and the reasons for its exclusion from the final analysis will be documented in the clinical study report (CSR).
- Nominal sample times will be used in the categorization of descriptive statistics.

- All postdose time points for which no sample is collected will be treated as missing.
 No value will be imputed for these missing values.
- Concentration data below the lower limit of quantitation (BLQ) will be defaulted to 0.00.

6 Data Analysis

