## 1.2 Clinical Pharmacokinetics of Dapson

Dapson absorption after once-daily ACZONE 7.5% administration in patients with acne vulgaris results in low systemic exposure to dapson and its metabolites. Systemic exposure to dapson from ACZONE 7.5% is expected to be about 1% of that from a typical oral dose of dapson 100 mg. Mean maximum plasma concentration ( $C_{max}$ ) and area under the plasma-concentration time curve from time 0 to 24 hours postdose of dapson at steady-state after once-daily dosing of dapson 7.5% were approximately 28.6% and 28.7% lower than those following twice-daily dosing of ACZONE 5%, respectively (NDA 21-794). The volume of distribution of dapson is about 1.5 to 2.5 L/kg. It is distributed throughout total body water and present in all tissues, especially liver, muscle, kidney, and skin. Its protein binding is 70% to 90%, and the acetylated dapson metabolite has a protein binding of ~99%. Dapson is acetylated by N-acetyl transferase in the liver to its major metabolite, N-acetyl dapson (NAD). The acetylation of dapson is reversible, resulting in a relatively constant ratio of NAD to dapson in plasma during the elimination phase. Dapson is also N-hydroxylated via cytochrome (CYP) P4502E1 and CYP3A4 to dapson hydroxylamine (DHA) in the liver, which appears to be responsible for the drug's hematologic toxicity. The  $C_{max}$  and area under the concentration-time curve for DHA are approximately 5% of those of the parent compound. The relationship between oral and topical exposure for DHA is expected to be similar to the relationship observed for the dapson parent compound. The apparent terminal half-life ( $T_{1/2}$ ) values of dapson and NAD are estimated to be similar and the mean/median values are in the range of 30 to 44 hours after multiple doses of dapson. The DHA is primarily excreted in urine (~85%), with a small percentage excreted in feces. Consistent

with lower systemic exposures, urinary excretion of DHA after topical dapsone is about 1% of that obtained with the oral formulation.

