7.1 Statistical Summarization

No formal inferential statistics will be performed with the PK data. Descriptive statistics (arithmetic mean, standard deviation, relative standard deviation, maximum, median, minimum) will be reported for peak and trough plasma concentrations of dapsone, NAD, DHA, and other metabolites or analytes (if warranted).

If warranted, graphical methods may be used to examine the relationships between systemic drug concentrations and the changes in lesion counts and safety parameters. Also, as appropriate, additional pharmacokinetic analysis by gender may be included in the final report.

8 Presentation of Final Results

All summarization will be done using Phoenix® WinNonlin® (version 6.3 or newer). Tabulations may be exported into Word 2010 (or newer) for formatting or exported to pdf.

9 References

FDA Letter 2016:

http://www.accessdata.fda.gov/drugsatfda docs/appletter/2016/207154Orig1s000ltr.pdf.

ALLERGAN

PK DAP 1679-401-006

Date (DD/MMM/YYYY)/Time (PT)

Signed by:

Justification

29-Jan-2018 16:27 GMT-080

PPD

PPD Approval

30-Jan-2018 10:08 GMT-080

PPD

PPD Approval

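### Setting concentrations below quantitation to zero can lower the mean plasma concentration, probably most for DHA, and the planned summaries do not show how many values were replaced

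*SAP*

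**What the plan says.** DAP 5.6 gives one rule for unquantifiable samples: "Concentration data below the lower limit of quantitation (BLQ) will be defaulted to 0.00". It belongs to a list that opens "Unless otherwise specified in subsequent sections, the general data handling include the following". The later DAP sections (6.1, 7.1 and 8) specify nothing different, so the rule covers every analyte at both timepoints.

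DAP 7.1 names the statistics to be reported for peak and trough concentrations: "arithmetic mean, standard deviation, relative standard deviation, maximum, median, minimum". The list contains neither n nor a count of BLQ values. SAP Table 5-2 does require a count of non-missing values for continuous summaries, but the SAP leaves pharmacokinetics to the DAP, and a count of non-missing values is not a count of BLQ values.

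Protocol 1.2 expects topical exposure to be about 1% of that from a 100 mg oral dose. It says that the Cmax and "area under the concentration-time curve for DHA are approximately 5% of those of the parent compound", and that DHA appears to be responsible for the drug's haematologic toxicity. On cohort size, DAP 5.1 says: "The PK Cohort will include at least 16 evaluable PK patients".

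**The concern.** Zero is a sensible entry for a sample drawn before the first dose, but the schedule has no such sample. The pre-dose draw at Week 1/Visit 3 follows at least seven scheduled daily applications (Days 1 to 7), and the second draw comes about 10 hours after the on-site dose that day. DAP 5.1 itself treats both as steady-state samples. A BLQ result here means low but unquantified. Entering 0.00 replaces a positive quantity with one known to be too small.

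Peak and trough concentrations are a stated study objective, and DAP 6.1 says that no PK parameters will be calculated, so these descriptive tables are the main PK result. Any error in the mean runs in the reassuring direction. The analyte where low values are easiest to foresee is the metabolite that the protocol links to toxicity. With 16 patients, each BLQ value is 1/16, or about 6%, of the sample.

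**Working it through.** **Inputs.** From the documents: the zero rule (DAP 5.6), the list of statistics (DAP 7.1), at least 16 evaluable patients (DAP 5.1), and DHA at about 5% of parent (Protocol 1.2). Not in the documents: any LLOQ, BLQ share, mean concentration or between-patient CV, or a level for N-acetyl dapsone (NAD). There is therefore no figure of the plan's own to reproduce. The CVs and BLQ shares below are assumptions.

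**Result that needs no model.** If k of n values are BLQ, each lies between 0 and the LLOQ. Zero substitution lowers the sample mean by more than nothing and by less than (k/n) × LLOQ. For 4 of 16, that is less than 0.25 × LLOQ. The mean with BLQ = 0 and the mean with BLQ = LLOQ therefore bracket the true sample mean, whatever the distribution.

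**Size under a lognormal assumption (true mean 1).** Let s² = ln(1 + CV²), and let z be the standard normal quantile of the BLQ share p. Then:
- LLOQ = exp(−s²/2 + s·z)
- relative bias with BLQ = 0: −Φ(z − s)
- with BLQ = LLOQ/2: add p·LLOQ/2; with BLQ = LLOQ: add p·LLOQ

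Worked case, CV 50% and p = 25%: s = 0.4724 and z = −0.6745, so z − s = −1.1469 and the bias is −Φ(−1.1469) = −12.6%. LLOQ = exp(−0.1116 − 0.3186) = 0.650, and p·LLOQ = 0.163. LLOQ/2 gives −12.6 + 8.1 = −4.4% (from unrounded values), and LLOQ gives −12.6 + 16.3 = +3.7%.

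Relative SD in the same case: the second moment is 1.25 × (1 − Φ(z − 2s)) = 1.25 × (1 − 0.0527) = 1.184 and the mean is 0.874. The SD is √(1.184 − 0.764) = 0.648, so the relative SD is 0.648/0.874 = 74%, against a true 50%.

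| BLQ share | Bias of mean, BLQ = 0, CV 50% | Bias of mean, BLQ = 0, CV 100% |
|---|---|---|
| 10% | −4.0% | −1.7% |
| 25% | −12.6% | −6.6% |
| 50% | −31.8% | −20.3% |

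**The bias may be negligible.** With the LLOQ at a quarter of the true mean, the bias is 0.0%, −0.3% and −1.9% at CV 40%, 60% and 100%.

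**Dapsone against DHA.** Assume a common LLOQ, DHA at 5% of parent and CV 60%:

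| LLOQ as % of dapsone mean | DHA share BLQ | Bias of DHA mean |
|---|---|---|
| 1% | 0.4% | −0.1% |
| 2.5% | 16.5% | −6.3% |
| 5% | 60.9% | −39.1% |

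The dapsone bias is about 0% in all three rows. If the DHA LLOQ were itself 5% of the dapsone LLOQ and the CVs were equal, the two relative biases would be equal.

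**Other statistics (simulation, n = 16, CV 60%).** With the LLOQ at half the true mean, the average relative SD rises from 0.56 to 0.70, the minimum is 0 in 94% of samples, the median is practically unchanged and the maximum is unchanged. With the LLOQ at the true mean, the median itself is 0 in 74% of samples.

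**The case against.** A reader might infer that the rule certainly understates exposure and that DHA certainly suffers most. The documents support neither as fact. If no sample is BLQ, the bias is exactly zero. DAP 5.1 reports that in an earlier maximal-use study of patients aged 11 or older, steady-state metabolite concentrations were relatively constant. That suggests they were usually quantifiable, although it gives no DHA level and does not exclude BLQ values. The 50% BLQ row is a scenario, not a forecast. For DHA to be worse than dapsone, its LLOQ must not be scaled down in proportion. Against NAD nothing can be checked. The 30-44 hour half-life in Protocol 1.2 is given for dapsone and NAD only. For DHA, the case against a true zero rests on its continued formation from parent.

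A second tempting reading is that the rule could hide high exposure in a child. It cannot: the maximum changes only if every value is BLQ, and the median essentially does not move while fewer than half are BLQ. Both are reported. Nor is the substitution invisible, since a minimum of 0.00 would show that BLQ values occurred. What stays hidden is how many.

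The analysis is also purely descriptive: "No formal inferential statistics will be performed with the PK data". At n = 16 the standard error of a mean is CV/√16, or 12.5-25% for a CV of 50-100%, so the biases up to 25% BLQ are about one standard error or less. That limits the importance of the point. It does not remove it, because this error always has the same sign.

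Finally, LLOQ/2 is also arbitrary. At CV 60% with the LLOQ at twice the true mean, it overstates the mean by 10.2%. The documents give no reason to make it the primary rule.

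**Conclusion.** The point holds as a conditional one. The rule is stated, is not overridden, and is applied to samples where a true zero is implausible. If any value is BLQ, the arithmetic mean falls, the relative SD tends to rise and the minimum becomes 0. Under lognormal data with CV 50-100%, the mean falls by 2-4%, 7-13% and 20-32% at 10%, 25% and 50% BLQ. With no BLQ values the fall is nil. That DHA is affected most is a reasonable inference from the 5% ratio if the LLOQs are similar, and no more than that. The maximum, and the median below 50% BLQ, remain reliable. The firm gap is in reporting: the listed statistics do not let a reader judge how far a mean depends on substituted zeros. This is a cheap improvement to a stated objective, not a flaw that undermines the study.

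**What to change.** Amend DAP 5.6 and 7.1, for each analyte and timepoint:

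- Report the LLOQ, n, and number (%) BLQ.
- Whenever any value is BLQ, show the mean with BLQ = 0 and with BLQ = LLOQ as bounds. LLOQ/2 may be added as a sensitivity value.
- Print a minimum or median that falls among BLQ values as `<LLOQ`, not 0.00.
- If more than half of the values are BLQ, report only the median (as `<LLOQ`), the maximum and the percent BLQ.

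This takes a few lines of text and one or two table rows, with no new data or visits. The downside is that the reader gets a range instead of a single mean when BLQ values occur. If none occur, the reported statistics are unchanged and the added counts show it.
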